1.7 Trial Conduct

This study will be conducted in compliance with the protocol approved by the Institutional Review Board, and according to Good Clinical Practice standards. No deviation from the protocol will be implemented without the prior review and approval of the IRB except where it may be necessary to eliminate an immediate hazard to a research subject. In such case, the deviation will be reported to the IRB as soon as possible.

1.8 Population

Patients with alcoholic hepatitis that will be recruited for this study should meet the following criteria:

CONFIDENTIAL

This material is the property of the Mayo Clinic. Do not disclose or use except as authorized.

- a. History of heavy alcohol abuse use: >40 g/day in females and >60 g/day in males for a minimum period of 6 months
- b. Consumed alcohol within 6 weeks of entry into the study
- c. Serum bilirubin > 3mg/dL AND AST >ALT, but less than 500 U/L
- d. MELD score range between 11-28. Patients with MELD scores 11-20 will be included in the first phase and patients with MELD scores 21-28 will be recruited for the second phase and escalation phase.

Patients with alcoholic hepatitis will be enrolled at approximately six clinical sites in the US. Additional sites may be added later to help accrual. The target number of participants to complete the study is 18 (see below).

STUDY NUMBERS:	
Phase I (MELD scores 11-20):	3+3+3 = 9
Phase II (MELD scores 21-28):	3+3+3 = 9
TOTAL participants:	18

Expected duration of patient participation is as follows:

Time expected for all patients to be enrolled:

- Approximately 3 years

Duration of individual patient participation:

- Up to 56 days (3 days Screening, 7-17 days of treatment, Follow up for 42 days following first dose)
- In the Dose Expansion Cohort, subjects receive 3 doses at approximately 7 day intervals. The duration of follow up will be for 56 days following first dose, or 42 days following third dose.

1.9 Power Calculation

As the primary outcome is observational, we have powered this study based upon the efficacy outcome, which is defined as a biochemical signal for success if AST/ALT is reduced by at least 30% on treatment. With no treatment, approximately 15-20% of patients reach this outcome following study drug treatment. We anticipate that a minimum of 50% will achieve this outcome. Using a conservative 2-sided assessment of superiority (50% with outcome vs. 20%), we will require 22 subjects to reach 80% statistical power.

For our efficacy outcome of AST/ALT, our primary analysis will assess a binary outcome of at least 30% reduction when on treatment. We will evaluate this with a 95% confidence interval of the percentage of subjects who have at least 30% reduction in AST/ALT on treatment, using an exact binary confidence interval. As a secondary analysis, we will use

CONFIDENTIAL

This material is the property of the Mayo Clinic. Do not disclose or use except as authorized.

robust linear regression with the change in AST/ALT at follow-up as compared to baseline as the outcome variable and baseline AST/ALT as the predictor. We will pair this analysis with a Bland-Altman plot. The goal of the secondary analysis is to assess the degree to which the reduction in AST/ALT attributable to treatment changes according to the subject's baseline AST/ALT. We will use 2-sides 5% type I error rate throughout.

2 *Study Objectives*

Primary:

- Assess the safety and tolerability and find the MTD of F-652 in patients with alcoholic hepatitis as determined by:
 - a. Absence of unexpected serious adverse events and,
 - b. Absence of worsening of alcoholic hepatitis (as determined by increase in MELD score > 5) up to Day 56 following administration of first dose of study drug.

Secondary:

- Determine the pharmacokinetics (PK) and pharmacodynamics (PD) of F-652 in patients with alcoholic hepatitis.

Additional:

- Assess the efficacy signal of F-652 in patients with alcoholic hepatitis as determined by:
 - a. Clinical: improvement in clinical status
 - b. Biochemical: Improvement in liver biochemistry, MELD and Lille scores at days 7, 28, 42 and 56
 - c. Biomarkers of IL 22 activity (CRP, SAA, triglycerides)

2.1 **Trial Design:**

The following study evaluations will be performed during the course of the Screening period (Day -3 to Day 0):

- Signed informed consent

CONFIDENTIAL

This material is the property of the Mayo Clinic. Do not disclose or use except as authorized.

- Inclusion and exclusion criteria
- Complete medical and surgical histories
- Record of concomitant medication usage, including use of prescription and over-the-counter medications, and vitamin and/or mineral supplements
- Patient demographics
- Completion of questionnaires: Alcohol Use Disorder Identification Test (AUDIT), Alcohol Use- NIAAA Six Question Set
- Alcohol consumption for the last 30 days assessed using the Timeline Follow Back Questionnaire
- Vital signs (blood pressure, pulse, respiratory rate, and temperature)
- Complete physical examination, including height, weight, and BMI
- 12-lead ECG
- Liver biopsy (if performed)
- Chest X-ray
- Assessment of MELD Score
- Calculate Maddrey Score
- Clinical chemistry, hematology, coagulation, lipid profile, CRP, SAA1 Nutritional Assessment and correction as necessary
- Evaluation by Addiction Services and Social Services to outline rehabilitation plan for alcohol abuse. This may include pharmacotherapy.
- Nutritional Assessment
- Immunogenicity Testing
- Urinalysis
- Serum pregnancy test (for women of childbearing potential)
- Collection of specimens (blood and urine) for bio-specimen banking (optional)

The following study evaluations will be performed during the course of Dosing Day 1 (± 1):

- Review of inclusion and exclusion criteria
- Update medical and surgical histories
- Assess for Adverse Events
- Update record of concomitant medication usage, including use of prescription and over-the-counter medications, and vitamin and/or mineral supplements
- Vital signs (blood pressure, pulse, respiratory rate, and temperature) pre-dose then 3 hours post-infusion with blood pressure and heart rate monitoring every 30 minutes. Weight and BMI
- Assessment of MELD Score and recording of Lille score parameters
- Clinical chemistry, hematology, and coagulation prior to study drug dosing
- Urine pregnancy test (for women of childbearing potential)
- Receive first dose of study drug
- Pharmacokinetic testing
- Confirmation that patient is abstinent from alcohol

The following study evaluations will be performed during Day 3 (± 1 day):

- Update medical and surgical histories
- Update record of concomitant medication usage, including use of prescription and over-the-counter medications, and vitamin and/or mineral supplements
- Update Adverse Events
- Vital signs (blood pressure, pulse, respiratory rate, and temperature)
- Weight and BMI
- Calculation of MELD Score
- Clinical chemistry, hematology, and coagulation
- Pharmacokinetic testing
- Confirmation that patient is abstinent from alcohol

The following study evaluations will be performed during the course of Dosing Day 7 (± 3 days):

- Update medical and surgical histories
- Update record of concomitant medication usage, including use of prescription and over-the-counter medications, and vitamin and/or mineral supplements
- Confirmation that patient is abstinent from alcohol
- Update Adverse Events
- Vital signs (blood pressure, pulse, respiratory rate, and temperature) pre-dose then 3 hours post-infusion with blood pressure and heart rate monitoring every 30 minutes.
- 12-Lead ECG
- Complete physical examination, including weight and BMI
- Calculation of MELD Score
- Calculation of Lille Score
- Clinical chemistry, hematology, coagulation, lipid profile, CRP, SAA1, total protein and albumin prior to study drug dosing
- Urine pregnancy test prior to study drug dosing
- Receive second dose of study drug
- Pharmacokinetic testing
- Collection of specimens (blood and urine) for bio-specimen banking
- Nutritional Assessment

The following study evaluations will be performed during the *Follow-up* Day 14 (± 3 days):

- Update medical and surgical histories
- Update record of concomitant medication usage, including use of prescription and over-the-counter medications, and vitamin and/or mineral supplements
- Confirmation that patient is abstinent from alcohol
- Update Adverse Events
- Vital signs (blood pressure, pulse, respiratory rate, and temperature)
- Weight and BMI

CONFIDENTIAL

This material is the property of the Mayo Clinic. Do not disclose or use except as authorized.

- Calculation of MELD Score
- Clinical chemistry, hematology and coagulation
- Pharmacokinetic testing
- Immunogenicity Testing
- Collection of specimens (blood and urine) for bio-specimen banking

The following study evaluations will be performed during the course of *Dosing Day 14* (± 3 days):

- Update medical and surgical histories
- Update record of concomitant medication usage, including use of prescription and over-the-counter medications, and vitamin and/or mineral supplements
- Confirmation that patient is abstinent from alcohol
- Update Adverse Events
- Vital signs (blood pressure, pulse, respiratory rate, and temperature) pre-dose then 3 hours post-infusion with blood pressure and heart rate monitoring every 30 minutes.
- 12-Lead ECG
- Complete physical examination, including weight and BMI
- Calculation of MELD Score
- Clinical chemistry, hematology, coagulation, lipid profile, CRP, SAA1, total protein and albumin prior to study drug dosing
- Urine pregnancy test prior to study drug dosing
- Receive third dose of study drug
- Pharmacokinetic testing
- Collection of specimens (blood and urine) for bio-specimen banking
- Nutritional Assessment

The following study evaluations will be performed during the follow-up *Day 28* (± 4 days):

- Update medical and surgical histories
- Update record of concomitant medication usage, including use of prescription and over-the-counter medications, and vitamin and/or mineral supplements
- Confirmation that patient is abstinent from alcohol
- Update Adverse Events
- Vital signs (blood pressure, pulse, respiratory rate, and temperature)
- Complete physical examination, including weight and BMI
- 12-Lead ECG
- Alcohol consumption for the last 30 days assessed using the Timeline Follow Back Questionnaire
- Calculation of MELD Score
- Clinical chemistry, hematology, coagulation, lipid profile, CRP, SAA1, total protein and albumin
- Pharmacokinetic Testing
- Immunogenicity Testing

CONFIDENTIAL

This material is the property of the Mayo Clinic. Do not disclose or use except as authorized.

- Collection of specimens (blood and urine) for bio-specimen banking.

The following study evaluations will be performed during Day 42 (± 2 days):

- Update medical and surgical histories
- Update record of concomitant medication usage, including use of prescription and over-the-counter medications, and vitamin and/or mineral supplements
- Confirmation that patient is abstinent from alcohol
- Update Adverse Events
- Vital signs (blood pressure, pulse, respiratory rate, and temperature)
- Weight and BMI
- Physical Examination
- Calculation of MELD Score
- Clinical chemistry, hematology, and coagulation
- Complete Timeline Follow-back Questionnaire
- Collection of specimens (blood and urine) for bio-specimen banking.
- Pharmacokinetic Testing
- Immunogenicity Testing
- Nutritional Assessment

The following study evaluations will be performed during Day 56 (± 2 days) (Only completed if patient received three doses of study drug):

- Update medical and surgical histories
- Update record of concomitant medication usage, including use of prescription and over-the-counter medications, and vitamin and/or mineral supplements
- Confirmation that patient is abstinent from alcohol
- Update Adverse Events
- Vital signs (blood pressure, pulse, respiratory rate, and temperature)
- Weight and BMI
- Physical Examination
- Calculation of MELD Score
- Clinical chemistry, hematology, and coagulation
- Complete Timeline Follow-back Questionnaire
- Collection of specimens (blood and urine) for bio-specimen banking.
- Nutritional Assessment

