Objectives	
 a. Assess the safety and tolerability of F-652 in patients with alcoholic hepatitis as determined by absence of unexpected serious adverse events up to Day 42 or Day 56 following administration of first dose of study drug. b. Determine the pharmacokinetics (PK) and pharmacodynamics (PD) of F-652 in patients with alcoholic hepatitis. c. Assess the efficacy signals of F-652 in patients with alcoholic hepatitis (compared to historical patient data) as determined by : 
 A. Clinical: improvement in clinical status B. Biochemical: Improvement in liver biochemistry, MELD and Lille scores at days 7, 28, 42 and 56. C. Biomarkers of IL 22 activity (CRP, SAA, triglycerides),
Number of Subjects	Up to 18 participants at approximately six sites.

CONFIDENTIAL

This material is the property of the Mayo Clinic. Do not disclose or use except as authorized.

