Statistical Methodology	
Detailed methodology for summary and statistical analyses of the data collected in this trial will be documented in a Statistical Analysis Plan, which will be implemented by the Indiana University Data Coordinating Center. This document will expand upon and may modify the plans outlined in the protocol; however, any major modifications of the primary endpoint definition and/or its analysis will also be reflected in a protocol amendment. In this cohort dose escalation study all statistical tests will be two-sided with no adjustment for multiplicity.
 
Descriptive summaries of variables will be provided where appropriate. For continuous variables, the number of non-missing values (n) and the median, mean, standard deviation, minimum, and maximum will be summarized. For categorical variables, the number and percent of each variable will be summarized. All collected data will be presented in listings.

1 Introduction

This document is a protocol for a human research study. This study will be carried out in accordance with the applicable United States government regulations and Mayo Clinic research policies and procedures. The described study will be conducted in compliance with the protocol, Good Clinical Practices standards and associated Federal regulations, and all applicable institutional research requirements.

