7.1 Statistical Methods

Primary endpoint (safety): The number and percentage of patients with SAE and increase in MELD score > 5 up to Day 56 following administration of first dose of study drug will be summarized by each dose level. Ninety-five percent confidence interval of the percentage will be calculated too.

Summary of adverse event will also be provided by each dose level.

Secondary endpoint: Pharmacokinetics (PK) and pharmacodynamics (PD) of F-652 in patients with alcoholic hepatitis at the first dose level (10ug/kg) and subsequent dose levels will be determined by the study sponsor using standard pharmacological tools. The total exposure (area under the curve), maximum serum concentration, time at maximum concentration, last measurable serum concentration, time at last measurable concentration, clearance, volume of distribution, elimination half-life, accumulation ratio and dose proportionality will be calculated.

Efficacy signal endpoint: The main efficacy end point is the reduction of AST/ALT or serum triglycerides. If patients show a reduction of AST/ALT or serum triglyceride by 30% at day 42, the drug shows efficacy in this patient. We will calculate the percentage of patients with efficacy (rate) and its 95% confidence interval for each dose level.

We will also use the proportion of patients with 30% change of AST, ALT from baseline to Day 3, Day7, Day14, Day 28, Day 42 and Day 56 as the dependent variable, dose level and baseline AST, ALT and other patients' characteristic at baseline as the covariates to evaluate the change (efficacy) or drug by dose level. A random intercept will be included for accommodating the correlation among the repeated measurement.

Other efficacy endpoints: Paired t-test or signed-rank test will be used to compare the level Lille score. Linear mixed-effect models will be used to analyze the MELD score, triglycerides, CRP, and SAA1 in a similar way to the AST/ALT.

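### Section 1.9 requires 22 subjects for 80% power, but the plan enrols 18 (about 76% exact power if all are evaluable and pooled), omits the powered analysis from Section 7.1, and leaves no room for the Section 1.6 expansions if all six cohorts run

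*Combined protocol and SAP*

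**What the plan says.** **Sample size.** Section 1.9 says the primary outcome is observational, so the study is powered on efficacy: an AST/ALT reduction of at least 30%. It puts the untreated rate at 15-20%, expects at least 50% on F-652, and concludes: "50% with outcome vs. 20%), we will require 22 subjects to reach 80% statistical power". The type I error is two-sided 5%. The Study Summary gives the number of subjects as "Up to 18 participants at approximately six sites". Section 1.8 says "The target number of participants to complete the study is 18 (see below" and builds that number as 3+3+3 in each of two MELD phases.

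**Analysis.** For AST/ALT, Section 1.9 says "We will evaluate this with a 95% confidence interval of the percentage of subjects who have at least 30% reduction in AST/ALT on treatment". The interval is to be an exact binomial one. Section 1.9 does not say whether doses and MELD phases are pooled. Section 7.1 says "The main efficacy end point is the reduction of AST/ALT or serum triglycerides". It then counts a patient as a success on a 30% reduction in AST/ALT or triglycerides at day 42, and gives a rate and 95% interval for each dose level. The Summary defers detail to a separate statistical analysis plan: "This document will expand upon and may modify the plans outlined in the protocol".

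**Expansions.** Section 1.6 adds 3 patients at any dose level with 1 dose-limiting toxicity (DLT) in 3, applies the same format in the second phase, and adds 6 at the maximum tolerated dose (MTD) if only 1 of 3 responds there.

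**The concern.** The protocol gives one number as what its power calculation requires and a smaller one as the most it will enrol. A reader of Section 1.9 would credit the trial with 80% power that 18 patients do not give under the plan's own inputs. That reader would also look in Section 7.1 for the analysis behind the power statement and find a different end point, a different time point and smaller groups.

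The ceiling raises a separate practical matter. Six cohorts of exactly 3 use all 18 places. If every cohort opens and an expansion is triggered, the Section 1.6 rule cannot be followed until the enrolment number has been changed.

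**Working it through.** **Inputs (Section 1.9):** reference rate 20% (the conservative end of 15-20%), expected rate 50%, two-sided 5%, exact interval. There is no concurrent control, so this is a one-sample comparison with a fixed rate. Assumed here: all patients evaluable, doses and MELD phases pooled.

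**1. Reproducing 22.** One-sample normal approximation with the variance taken at 50%:

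n = (1.960 + 0.8416)² × 0.5 × 0.5 / (0.50 − 0.20)² = 7.849 × 0.25 / 0.09 = 21.8, so 22.

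The same formula gives power Φ(0.30√n / 0.5 − 1.960):

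- n = 22: Φ(2.814 − 1.960) = 80.4%
- n = 18: Φ(2.546 − 1.960) = 72.1%

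With the null variance in the alpha term, n = (1.960 × √0.16 + 0.8416 × √0.25)² / 0.09 = 16.1, so 17 (power 83.6% at 18). That version is not the source of 22. A two-arm reading needs 39 per arm and does not fit either.

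**2. Power under the exact interval that 1.9 names.** For each n, find the fewest responders whose exact 95% lower limit exceeds 20% (upper tail at 20% no more than 2.5%), then the chance of at least that many at a true rate of 50%.

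| n | Responders needed | Upper tail at 20% | Power at 50% |
|---|---|---|---|
| 17 | 8 | 1.09% | 68.5% |
| 18 | 8 | 1.63% | 76.0% |
| 19 | 8 | 2.33% | 82.0% |
| 20 | 9 | 1.00% | 74.8% |
| 21 | 9 | 1.44% | 80.8% |
| 22 | 9 | 2.01% | 85.7% |
| 23 | 10 | 0.89% | 79.8% |
| 24 | 10 | 1.26% | 84.6% |
| 27 | 11 | 1.10% | 87.6% |

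At n = 18, 7 responders give an interval of 17.3% to 64.3%, which includes 20%; 8 give 21.5% to 69.2%, which excludes it. Power rises and falls with n because the responder threshold moves in whole patients.

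**3. Sensitivity at n = 18.** Power reaches 80% at a true rate of about 51.6%. Against a 15% reference, 7 responders suffice (upper tail 1.18%) and power is 88.1%.

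**4. The powered analysis against what 7.1 provides.**

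| | Section 1.9 | Section 7.1 |
|---|---|---|
| End point | AST/ALT alone | AST/ALT or triglycerides |
| Time | on treatment | day 42 |
| Group | not stated | each dose level |
| Interval | exact 95% | 95%, method not named |

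For scale, take AST/ALT response in 6 patients at one dose (3 per phase, both phases combined). The upper tail at 20% is 9.9% for 3 or more responders and 1.7% for 4 or more, so 4 of 6 are needed. Power at 50% is (15 + 6 + 1)/64 = 34.4%. No reference rate is given for the composite, so its power cannot be worked out.

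**5. Enrolment if all six cohorts run.**

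- No expansion: 6 × 3 = 18
- One DLT expansion: 18 + 3 = 21
- Response expansion: 18 + 6 = 24
- Both: 18 + 3 + 6 = 27, and more with further DLT expansions

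**The case against.** The strongest reply is that little power is at stake. Efficacy is listed as an additional objective, and cohorts of 3 follow from the escalation rule, not from a power target. Against a 15% reference, 18 patients give 88.1%. Under the exact interval, 19 patients already reach 80%. If an expansion is honoured, the pooled number rises to 21 or 24 and exact power to 80.8% or 84.6%. A separate analysis plan may also supply the pooled analysis. All of this stands, and it limits the weight of the point. It does not remove the contradiction: Section 1.9 makes efficacy the sole basis for the sample size, chooses 20% as its reference and asks for 22. The text supplied contains no later plan that resolves it.

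A reader might infer more than the documents support:

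- *That 22 is miscalculated.* It reproduces.
- *That power falls by nearly ten points, from 85.7% to 76.0%.* The plan claims 80%, not 85.7%, and 22 is a local peak of the exact curve. The shortfall is 80 − 76.0 = 4.0 points exact, or 80.4 − 72.1 = 8.3 points by the approximation behind 22.
- *That any expansion must breach the ceiling.* This holds only if all six cohorts run. If the response expansion fails in the first phase and the study ends there, enrolment is 9 + 6 = 15. The third-dose patients may already be counted in the final cohort, so they need not add to the total.
- *That the MTD definition on 6 patients wholly conflicts with cohorts of 3.* After 1 DLT in 3, Section 1.6 plainly adds 3 more. It is silent only where 0 of 3 have a DLT at the top dose.

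**Conclusion.** The point holds as an internal inconsistency that should be corrected. The stated 80% belongs to 22 subjects, and the plan enrols 18. For a true rate of 50% against 20%, power at 18 is 76.0% (exact) or 72.1% (approximation), provided that all 18 are evaluable, doses and phases are pooled, and no expansion occurs. No allowance for non-evaluable patients is stated; losing one gives 68.5%. The documents do not confirm pooling, so 76.0% is conditional on it.

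The analysis to which the power refers is missing from Section 7.1. The ceiling of 18 is incompatible with any Section 1.6 expansion when all six cohorts are run. None of this undermines the safety objective.

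**What to change.** 1. **Restate Section 1.9 for the planned size.** Suggested wording, if the sponsor confirms that pooling is intended: *With 18 evaluable patients pooled over doses and MELD phases and no expansion, an exact 95% confidence interval excludes 20% with about 76% power at a true AST/ALT response rate of 50%, and with 80% power at about 52%.* If the sponsor prefers to keep 22, the Summary and Section 1.8 must plan 22 evaluable patients, 4 more than now. Under the exact interval 19 or 21 would also reach 80%; 20 and 23 would not.

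2. **Put the Section 1.9 AST/ALT exact interval in Section 7.1** as the analysis to which the power refers, with its time point (1.9 says on treatment, 7.1 day 42, 1.6 day 42 or 56). State that the power does not extend to the per-dose intervals or to the composite. Separately, reconcile the composite's day 42 triglycerides with the collection schedule. Section 5.2 and the lipid row of the Schedule of Procedures show none at day 42, although the laboratory footnote lists the lipid profile under serum chemistry, which is drawn at every visit.

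3. **Reconcile the Summary and Section 1.8 with Section 1.6.** Give a base number (18) and a maximum that includes the conditional additions. Settle how the MTD definition on 6 patients applies where 0 of 3 have a DLT at the top dose.

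**Cost.** Item 1 is wording, unless 22 is kept. Item 2 adds one analysis of AST/ALT data already collected; the triglyceride question may need a change to the schedule or to the end point. Item 3 changes the enrolment number and needs IRB approval; drug supply and accrual time depend on the maximum chosen.

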Diagnosis and Main Inclusion Criteria	
Alcoholic hepatitis is a syndrome of progressive inflammatory liver injury associated with long-term heavy intake of ethanol. The pathogenesis is not completely understood⁷. Patients who are severely affected present with subacute onset of fever, hepatomegaly, leukocytosis, marked impairment of liver function (e.g., jaundice, coagulopathy), and manifestations of portal hypertension (e.g., ascites, hepatic encephalopathy, variceal hemorrhage). However, milder forms of alcoholic hepatitis often do not cause any symptoms.
 
To participate in this study, patients must meet all of the following criteria:
 
 1. Able to provide written informed consent (either from patient or patient's legally acceptable representative) 2. Male or female patients 21 years of age or older 3. Patients with alcoholic hepatitis defined as: 
 a. History of heavy alcohol abuse use: >40 g/day in females and >60 g/day in males for a minimum period of 6 months AND b. Consumed alcohol within 6 weeks of entry into the study AND c. Serum bilirubin > 3mg/dL AND AST >ALT, but less than 500 U/L d. MELD score between 11-28 e. Liver biopsy will be carried out to confirm diagnosis in all patients except those who meet criteria a-c and in whom other causes of liver disease have been excluded (viral, drug, autoimmune etc). 4. Women of child-bearing potential must utilize appropriate birth control. 
*Patients on steroids and/or pentoxifylline will not be excluded from the study.

Study Product, Dose, Route, Regimen	F-652 with a dose escalation regimen using 10 µg/kg, 30 µg/kg and 45 µg/kg.
Duration of Administration	Participants will be given a dose of F-652 on Day 1 and Day 7 of the study. Following demonstration of safety with the Day 1 and Day 7 dose in the patient group with MELD score 21-28, a 3rd dose of the maximum tolerated dose will be administered on Day 14
Reference therapy	There is not a standard reference therapy or placebo against which the study product is being compared.

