2.2 Study Design/Type

Schedule of Procedures

Safety Assessments	Screening (-72 hrs)	Day 1 (± 1 day)	Day 3 (± 1 day)	Day 7 (± 3 days)	Day 14 (± 3 days)	Day 28 (± 4 days)	Day 42 (± 2 days)	Day 56 ⁶ (± 2 days)
Inclusion/Exclusion Criteria	X	X						
Physical Examination	X			X	X ⁵	X	X	X
Medical/Surgical History	X		X	X	X	X	X	X
Nutritional Assessment	X				X ⁵		X	X
AUDIT and NIAAA Questionnaires	X							
Timeline Followback Questionnaire	X					X	X	X
Vital Signs	X		X		X	X	X	X
Serial Vital Signs		X		X	X ⁵			
Serum Chemistry ^A	X	X	X	X	X	X	X	X
Coagulation ^A	X	X	X	X	X	X	X	X
Hematology ^A	X	X	X	X	X	X	X	X
Serum pregnancy test	X							
Urine pregnancy test		X		X	X ⁵			
Lipid profile, CRP, SAA1, total protein, albumin ^A	X			X	X ⁵	X		
Calculate MELD Score	X	X	X	X	X	X	X	X
Calculate Lille Score				X				
Calculate Maddrey Score	X							
Urinalysis ¹	X							
ECG ²	X			X	X ⁵	X		
Chest X-ray ³	X							
Adverse Events		X	X	X	X	X	X	X
Concomitant Medications	X	X	X	X	X	X	X	X
Study Drug Dosing		X		X	X ⁵			
Pharmacokinetic Sample Collection ⁷		X	X	X	X	X	X	
Immunogenicity Testing ⁸	X				X	X	X	
Biomarkers(blood and urine)	X ⁷			X	X	X	X	X
Confirmation that patient is abstinent from alcohol		X	X	X	X	X	X	X

1. Urinalysis results can be used for Screening if tested within 7 days.
2. ECG results can be used for Screening if tested within 7 days.
3. Chest X-ray results can be used for Screening if tested within 30 days.
4. Day 1, Day 7 and Day 14 labs and testing must be completed prior to dosing.
5. These tests/procedures will occur only on Day 14 if the patient is receiving a 3rd dose at that visit.
6. Day 56 will only occur if the patient received a 3rd dose on Day 14.
7. Biomarkers are optional at Screening.

^AClinical Laboratory Tests

Hematology	Coagulation	Serum Chemistry		Urinalysis	Other
		Liver Function Tests	Other Chemistry		
Complete Blood Count with differential, Platelet count, MCV	PT, INR	AST, ALT, Total Bilirubin, Direct Bilirubin	Sodium, Potassium, Chloride, Bicarbonate, Calcium, Magnesium, Phosphate, Creatinine, BUN, Glucose, Total protein, Albumin, Lipid profile, CRP, SAA1	Specific gravity, pH, Blood, Protein, Glucose, Ketones	β-HCG serum pregnancy test Urine pregnancy test

Blood will be collected for PK sampling per the schedule below:

⁸Pharmacokinetic Sampling Schedule

Study Visit Day					Study Visit Day +0*	Study Visit Day +2*	Study Visit Day +3*	Study Visit Day +4*
					24 hrs	48 hrs	72 hrs	96 hrs

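### The secondary AST/ALT regression in section 1.9 has baseline on both sides, so regression to the mean alone gives a negative slope that the plan would read as a treatment effect varying with baseline (minor; exploratory analysis only)

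*Combined protocol and SAP*

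**What the plan says.** Section 1.9 makes a binary outcome, at least a 30% reduction in AST/ALT, its main efficacy analysis, with an exact 95% interval. It then adds a secondary analysis: "robust linear regression with the change in AST/ALT at follow-up as compared to baseline as the outcome variable and baseline AST/ALT as the predictor", shown together with a Bland-Altman plot. The stated goal is to "assess the degree to which the reduction in AST/ALT attributable to treatment changes according to the subject's baseline AST/ALT". The section closes with "We will use 2-sides 5% type I error rate throughout".

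The trial is single-arm. Under Reference therapy, the Study Summary says "There is not a standard reference therapy or placebo against which the study product is being compared". Its Objectives mention historical patient data for the efficacy signals, but 1.9 does not connect such data to this regression.

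Section 1.9 does not say whether change is in U/L, percent or logs, whether AST/ALT means each enzyme or their ratio, or which draw is baseline. Two pre-dose chemistry draws are scheduled. One is at Screening (Day -3 to Day 0). For the other, the Day 1 list in 2.1 has "Clinical chemistry, hematology, and coagulation prior to study drug dosing", and footnote 4 to the schedule in 2.2 adds "Day 1, Day 7 and Day 14 labs and testing must be completed prior to dosing". Section 5.2, however, lists AST and ALT without Day 1 and with a Day 35 that has no column in the schedule.

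Section 7.1 does not repeat the regression. Neither section mentions regression to the mean.

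**The concern.** The follow-up-minus-baseline change contains the baseline value with a minus sign, and the same value is the predictor. A patient whose baseline draw happens to be high tends to show a larger fall, and one whose draw happens to be low a smaller fall, whatever the drug does. The regression therefore tends to slope downward when the effect is the same at every true baseline.

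The stated goal invites a reader to take such a slope as a larger drug effect in patients with higher enzymes. Attribution to treatment is also unsupported on other grounds. There is no comparator, section 1.1 expects slow resolution once drinking stops, and 1.9 itself sets its target against a 20% response rate without the drug. What is at stake is how one exploratory result is read.

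**Working it through.** **The plan's own figure.** The only sample-size figure in 1.9 is 22 subjects, for 50% against 20%. It reproduces: (1.960 + 0.842)² × 0.5 × 0.5 / 0.3² = 21.8, so 22. It concerns the responder analysis. The plan gives no figure for the regression.

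**Inputs from the documents.** n = 18 (target in 1.8); two-sided 5% and the 30% threshold (1.9).

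**Assumptions, because the documents give none of these.** Log scale; observed baseline SD 0.45; reliability of a single baseline value (the share of its variance that is true between-patient difference) 0.5 to 0.95; between-patient SD of log response 0 (uniform effect) or 0.3, unrelated to true baseline.

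**Expected slope.** Let baseline X = T + e and follow-up F = T + d + r + f. Here T is the true value, d the mean effect, r the individual response, and e and f independent errors. Then

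- F - X = d + r + f - e
- Cov(F - X, X) = -Var(e)
- slope = -Var(e)/Var(X) = reliability - 1

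The variation in response, r, drops out of the slope. It only widens the interval.

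**Simulation** (20,000 runs per setting, least squares, effect independent of true baseline):

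| Assumed reliability | 0.5 | 0.7 | 0.9 | 0.95 |
|---|---|---|---|---|
| Expected slope | -0.50 | -0.30 | -0.10 | -0.05 |
| Rejects slope = 0, uniform effect | 59% | 36% | 14% | 10% |
| Rejects slope = 0, response SD 0.3 | 42% | 22% | 8% | 6% |

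At reliability 0.9 and response SD 0.3, the bias of -0.10 compares with a mean 95% interval half-width of 0.42.

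**Robust fitting.** With a uniform effect, or none, Huber regression rejected in 57 to 63%, 36 to 41%, 15 to 17% and 10 to 12% of runs (two sets, 2,000 and 1,000 runs). That is no improvement.

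**Scale.** If AST and ALT are each analysed in U/L, an identical 30% fall in every patient means change = -0.30 × baseline. The slope is then exactly -0.30 with no measurement error at all. That is a true statement about U/L, but it does not show that the percentage fall depends on baseline. If AST/ALT means the ratio, an equal percentage fall in both enzymes leaves the ratio unchanged and this argument does not apply.

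**What the two pre-dose draws could do.**

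- *Log change from Day 1 regressed on the log Screening value.* With independent visit errors the null slope is 0, but a true slope is multiplied by the reliability: -0.30 is estimated at about -0.15, -0.21, -0.27 and -0.29. At reliability 0.9 and response SD 0.3, detection of a true -0.30 is about 26%, against about 46% as planned, the latter inflated by the bias. If 80% of the error variance is shared by the two visits, the null slope is -0.8 × (1 - reliability), which is -0.40, -0.24, -0.08 and -0.04.
- *Averaging the two draws.* With independent errors the null slope becomes -0.33, -0.18, -0.05 and -0.03. With 80% shared error, rejection at reliability 0.5 (uniform effect) falls only from 59% to about 54%.

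Shared error is plausible, since the draws are at most a few days apart.

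**The case against.** The strongest case against making much of this has several parts.

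- **It is exploratory.** Efficacy signals are listed under additional objectives in section 2, and 7.1 omits the regression. This stands and sets the grade. A reader might infer that dose escalation or the trial's efficacy conclusion is compromised. The documents do not support that: the response rule in 1.6 and the analysis in 1.9 count individual 30% reductions, and neither uses the slope.
- **No test of the slope is stated.** The goal is worded as estimation. This stands: a test against zero is inferred from the blanket 5% statement. A reader might take 59% as the plan's false-positive rate, but the documents support neither the test nor the reliability behind it. The bias in the estimate needs no test.
- **The uniform-effect row is the least natural,** because the trial covers three dose levels and two MELD strata. This also stands, and it is why the response SD 0.3 row is shown.
- **The Bland-Altman plot plots difference against average, which removes the coupling when the two variances are equal.** This stands only in part. The plan gives the plot no inferential role. At reliability 0.9 and response SD 0.3, regressing on the average gives (0.2925 - 0.2025)/2 ÷ 0.2149 = +0.21 with no true dependence, rejected in about 19% of runs.
- **A later SAP is promised,** which may expand or modify the protocol (Study Summary, Statistical Methodology). Scale and baseline could properly be settled there. The promise does not correct a regression and a reading that 1.9 already states.
- **AST/ALT may be a ratio.** Section 1.1 uses it that way in the biopsy criteria, while 7.1 speaks of AST and ALT. Section 1.9 does not settle it, so the U/L argument is conditional.

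**Conclusion.** Wrong as written, but minor. On the log scale the slope is biased by reliability minus 1 whenever the effect does not depend on true baseline. The plan's stated reading of the slope does not allow for this, and nothing in a single-arm design supports attributing the reduction to treatment.

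The direction follows from the algebra; the size rests on an assumed reliability. The bias is large at 0.5 to 0.7. At 0.9 or above it is small beside the uncertainty once response varies between patients. The rejection rates apply only if the slope is tested against zero.

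Nor does it follow that any negative slope would be pure artefact. A real dependence on baseline may exist; the planned regression cannot tell the two apart.

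**What to change.** In section 1.9 and the SAP:

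1. Replace 'attributable to treatment' with 'observed on treatment' and label the slope exploratory. State that regression to the mean alone gives a negative slope, so a slope different from zero is not evidence that the effect depends on baseline. This caveat holds whatever the reliability.
2. Analyse AST and ALT each as log(follow-up/baseline), which fits the way 7.1 names them, and say which draw is baseline.

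Optional sensitivity analysis, using draws already scheduled: regress log change from Day 1 on the log Screening value. State that it has lower power, attenuates a true slope, and does not remove error shared by the two visits. Averaging the two pre-dose draws is likewise only a partial reduction. If Day 1 is used, reconcile the AST/ALT time points in 5.2 (no Day 1, Day 35 listed) with 2.1 and 2.2.

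Cost: one paragraph in 1.9 and the SAP, and a line in 5.2 if Day 1 is used. No new blood draws are needed. The downside is a less favourable reading of the slope and a little more analysis.
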